1.2 Clinical Data to Date

A retrospective review of 12 women with twin pregnancies who underwent a physical exam-indicated cerclage (dilated cervix on examination or membranes visible at the external cervical os on speculum examination) during the second trimester were compared with 31 singleton pregnancies undergoing the same procedure from 1997 to 2012.²⁵ Comparing twins to singletons, the median time from cerclage placement to delivery was similar (92 vs. 106 days, p=0.3), as was the median GA at delivery (33.5 vs. 35.0 weeks, p=0.2). The likelihood of delivery at >32 weeks (75.0% vs. 71.0%, p>0.9) and the likelihood of neonatal survival to discharge (83.3% vs. 83.9%, p>0.9) were also similar. A case report of 4 women with twin pregnancy and cervical dilation with bulging membranes gave birth on an average of 48.5 days after cerclage placement.²⁶ A more recent publication evaluated 104 women with twin pregnancy vs. 334 singleton pregnancies with dilated cervix, median gestation at delivery was (31.9 weeks vs. 32.7 weeks) and delivery before 28 weeks (33.7% vs. 35.8%, P = .69) respectively.²⁸ **None of these publications have had an appropriate control group: twin gestation with expectant management.** Only one small retrospective cohort study had a control group with expectant management,²⁷ 23 women were identified with twin pregnancy, cervical dilation and visible membranes between 16-24 weeks; 16 underwent physical exam indicated cerclage while 7 received expectant management (control). In the control group 50% of the women were delivered prior to 24 weeks. Interval from time at diagnosis to delivery was significantly prolonged by approximately 6.8 weeks in the cerclage group, they had significant decreased SPTB ≤28 weeks (31.2% vs. 85.7% p=0.02) and increased neonatal survival upon discharge 71.8% vs. 42% (p=0.1).

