1.3 Risk/Benefits

Major risks of physical exam indicated cerclage that have been reported in previous studies involving singleton pregnancies and include intraoperative rupture of membranes between 4% and 15%, cervical laceration, bleeding, chorioamnionitis (undiagnosed at the time of cerclage or acquired posteriorly to its placement due to exposed membranes into the vaginal flora), failure to place the cerclage due to advanced cervical dilation and failure of the cerclage on prolonging pregnancy with possible pregnancy loss or delivery at a perivable gestational age around 23-26 weeks of gestation.^{23, 24, 29-32} Other risks of cerclage are those associated with anesthesia during the surgical procedure: hypotension, allergy to medications, post spinal headache. After the cerclage placement other risks maybe present during the following weeks as preterm contractions with the cerclage in place may cause laceration of the cervix and bleeding or preterm premature rupture of membranes in which case the cerclage needs to be removed.

Minor side effects include increased noninfectious vaginal discharge: there is a theoretical disruption the vaginal flora associated with foreign object, and minimal discomfort at the time of cerclage removal.

The potential benefits include prolongation of pregnancy, decreasing very preterm delivery (< 28 weeks), very low birth weight (<1500 grams), low birth weight (<2500 grams) and decreased neonatal morbidity (admission to the intensive care unit, respiratory distress, need of intubation, necrotizing enterocolitis, intraventricular hemorrhage), neonatal mortality and long term disease or disability associated with prematurity. These potential benefits are based on results of previous retrospective cohorts of available research in singletons and case reports in twin pregnancies. These benefits significantly outweigh the risk of having a complication related to cerclage placement.

Measurement to decreased risks associated to the cerclage: All of the investigators have received formal training on physical exam indicated cerclage placement. The training and experience of the investigators will minimize the risks associated with cerclage placement.

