2.2 Secondary Objective

To determine if cerclage reduces the incidence of spontaneous PTB <28 weeks and <32 weeks in asymptomatic women with twin gestations and dilated cervix diagnosed on pelvic exam between 16 to 23 6/7 weeks of gestation

To determine if cervical cerclage reduces the incidence of neonatal admission to the neonatal intensive care unit, decrease length of stay in the neonatal intensive care unit, decrease neonatal disease or death associated with prematurity in asymptomatic women with twin gestations, dilated cervix and visible membranes diagnosed on pelvic exam between 16 to 23 6/7 weeks of gestation

3 Study Design

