3.3 Secondary Study Endpoints

Secondary effectiveness endpoints:

- Gestational age at delivery
- Interval between diagnosis and delivery
- Birth weight of each neonate
- Spontaneous preterm birth rates at less than 24, 28, 32 and 37 weeks gestation
- Spontaneous rupture of membranes before 34 weeks gestation

Secondary safety endpoints:

- Admission to the NICU and length of stay
- Neonatal death before discharge
- Composite adverse neonatal outcome (includes necrotizing enterocolitis, Intraventricular hemorrhage (grade 2 or higher), respiratory distress syndrome, retinopathy, treatment for sepsis and neonatal death)
- Chorioamnionitis (clinical or histological)
- Significant adverse maternal effects including intraoperative rupture of membranes, bleeding and cervical laceration (tear).

4 Subject Selection and Withdrawal

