7.2 Statistical Methods

The primary outcome is spontaneous preterm birth before 34 weeks of gestation. Secondary outcomes include gestational age at delivery, interval between diagnosis and delivery, birth weight, spontaneous preterm birth rates at less than 24, 28, 32 and 37 weeks gestation, clinical chorioamnionitis and spontaneous rupture of membranes at less than 34 weeks gestation. Secondary safety outcomes include admission to NICU, neonatal death, length of stay in the NICU until discharge home, composite adverse neonatal outcome that includes necrotizing enterocolitis, intraventricular hemorrhage (grade 2 or higher), respiratory distress syndrome, retinopathy of prematurity and treatment for sepsis), and significant adverse maternal effects will include: intraoperative rupture of membranes, chorioamnionitis, postpartum hemorrhage (estimated blood loss and requirement of blood transfusion, cervical tear and uterine rupture).

Statistical analysis will be based on the intention-to-treat principle.

Comparisons between the two groups will be made with the Mann-Whitney U test. Univariate comparisons of dichotomous data will be performed with Fishers exact test. The p values for all hypotheses will be two sided, and p values of less than 0.05 will be considered to be significant. The risk of spontaneous preterm birth before 34 weeks will be quantified by use of the relative ratio and 95% CI. Multivariate analysis will be performed using logistic regression. The risk of spontaneous preterm birth from randomization until 34 weeks will be assessed with Kaplan-Meier analysis, in which gestational age

is the timescale, spontaneous delivery is the event, and elective deliveries are censored. SPSS software package (version 16.0) will be used for all statistical analyses.

8 Safety and Adverse Events

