1. Maternal sepsis with admission to ICU attributable to the cerclage placement
2. Maternal death attributable to the cerclage placement
3. Maternal bleeding requiring blood transfusion attributable to cerclage placement
4. Fetal and/or neonatal death or injury attributable to the cerclage placement

Frequency of monitoring reports: after approximately 50% of the subjects have delivered

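### No endpoint compares fetal loss or stillbirth between the arms, so the neonatal-death comparison can understate, and under some splits of losses reverse, a survival benefit of cerclage

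*Combined protocol and SAP*

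**What the plan says.** Section 3.3 lists "Neonatal death before discharge" among the secondary safety endpoints. Section 7.2 has "Secondary safety outcomes include admission to NICU, neonatal death, length of stay in the NICU until discharge home", with no time window for death. Neither section defines neonatal death or says whether the denominator is live births, all fetuses or women.

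The composite does not fill the gap. Its list in 3.3 ends "respiratory distress syndrome, retinopathy, treatment for sepsis and neonatal death". The list in 7.2 ends "respiratory distress syndrome, retinopathy of prematurity and treatment for sepsis" and names no death at all. Neither includes fetal loss. Objective 2.2 asks whether cerclage can "decrease neonatal disease or death associated with prematurity".

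Fetal death appears once, in the event list of 8.2: "Fetal and/or neonatal death or injury attributable to the cerclage placement".

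The randomisation window is 16 0/7 to 23 6/7 weeks. Section 1.3 names "possible pregnancy loss or delivery at a perivable gestational age around 23-26 weeks of gestation" among the risks when a cerclage fails. Of the one cited series with an expectant group, 1.2 says: "In the control group 50% of the women were delivered prior to 24 weeks". Section 6.5 has the pregnancy outcome, and the newborn outcome up to discharge, abstracted from the records.

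**The concern.** On the ordinary meaning of the term, a neonatal death requires a live birth. Treatment affects whether a fetus is born alive: the hypothesis in 1.1 is that cerclage prolongs pregnancy. A fetus lost at 20 weeks in the expectant arm adds nothing to the numerator. A co-enrolled fetus carried to 26 weeks by a cerclage becomes a neonate at risk of death. The comparison then no longer covers everyone randomised, which sits badly with the intention-to-treat analysis in 7.2.

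At stake is the mortality result, which families and clinicians are likely to look at closely. A real gain in survival could appear smaller than it is, absent, or as an excess of deaths. Because the term is undefined, the result could also turn on how each site of an open-label, multi-centre trial classes a previable twin with brief signs of life.

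**Working it through.** **The plan's own figures.** No rate or power is stated for mortality. The sample size concerns the primary endpoint only and reproduces: 80% against 40%, two-sided 5%, 80% power, no continuity correction gives 23 per arm, and 46/0.9 rounds up to 52.

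**Inputs from the controlled series in 1.2** (16 cerclage, 7 expectant women). Survival is printed as 71.8% and 42%. These fit 23/32 = 71.9% and 6/14 = 42.9%, that is, all fetuses of 16 and 7 women. Total loss is therefore 9/32 = 28.1% against 8/14 = 57.1%.

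**Formulas.** Let S be survival per fetus and L the share of fetuses lost before live birth.
- Neonatal deaths per fetus = 1 − S − L
- Neonatal deaths per live birth = (1 − S − L)/(1 − L)

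**Assumptions on L.** The documents do not say which deliveries before 24 weeks were live births; treating all of them as losses before live birth is an assumption. The printed 50% is not a whole number of 7 women, so 3/7 and 4/7 are shown as well. No such figure is given for cerclage. I take 1/16 to 4/16 of the women, both fetuses lost; 5/16 would be 10/32 fetuses, more than the 9/32 lost in total.

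| Arm | L | Per live birth | Per fetus |
|---|---|---|---|
| Expectant | 3/7 = 42.9% | 0.143/0.571 = 25.0% | 14.3% |
| Expectant | 50% | 0.071/0.500 = 14.3% | 7.1% |
| Expectant | 4/7 = 57.1% | 0% | 0% |
| Cerclage | 1/16 = 6.25% | 0.219/0.938 = 23.3% | 21.9% |
| Cerclage | 2/16 = 12.5% | 0.156/0.875 = 17.9% | 15.6% |
| Cerclage | 3/16 = 18.75% | 0.094/0.813 = 11.5% | 9.4% |
| Cerclage | 4/16 = 25% | 0.031/0.750 = 4.2% | 3.1% |

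**Reading the table.**
- Expectant L = 50%: cerclage looks worse per live birth when its own L is below 0.138/0.857 = 16%, and per fetus when it is below 0.281 − 0.071 = 21%. Above those values a benefit shows.
- Expectant L = 3/7: no reversal per live birth anywhere in the assumed range (25.0% against 23.3% to 4.2%). Per fetus, the two lowest cerclage shares still reverse (14.3% against 21.9% and 15.6%).
- Expectant L = 4/7: the expectant arm has no neonatal deaths, so cerclage looks worse throughout.

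**At the trial's size.** With 52 fetuses per arm, the same loss rates give about 30 expectant and 15 cerclage losses.
- If 26 and 5 of these (5 is assumed) precede live birth, the counted neonatal deaths are 4 against 10: 4/52 = 7.7% against 10/52 = 19.2% per fetus, and 4/26 = 15.4% against 10/47 = 21.3% per live birth.
- For cerclage to look equal or worse per fetus, the expectant arm needs at least 15 more losses before birth than the cerclage arm. Per live birth, it needs at least 22 such losses in the expectant arm.
- If the same share of losses precedes birth in both arms (checked from 0 to 90%), there is no reversal, but the difference shrinks. At one half it is 15/52 = 28.8% against 7.5/52 = 14.4% per fetus, 14 points rather than 29.

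**The case against.** Several stronger readings are tempting, and the documents do not support them.

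- **That a fetus lost after randomisation can never count as a death.** Neonatal death is undefined, and a previable twin born alive who then dies would count on the ordinary meaning. The survival figures quoted in 1.2 are labelled neonatal yet fit a denominator of all fetuses. What can be shown is that fetal loss is not named in any endpoint and that the term and denominator are open.
- **That the endpoint is always biased against an effective cerclage.** Reversal depends on the split of losses. Per live birth, moving from 3/7 to 4/7 expectant women changes the sign, which is one woman in a series of seven.
- **That 8.2 contradicts 3.3.** The item in 8.2 is a reporting item limited to events attributed to the cerclage. A different scope there is not a contradiction. For the same reason it cannot supply a comparison with expectant management.
- **That the endpoint cannot answer objective 2.2.** That objective is itself worded as neonatal death, so the endpoint matches it. The objective is narrow in the same way.

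It is also fair to say that previable deliveries are not hidden. Spontaneous birth before 24 weeks, gestational age at delivery and the interval from diagnosis to delivery are all secondary endpoints, and would be reported beside the neonatal deaths. This narrows the gap without closing it. Those endpoints record timing, not death, and the 24-week rate covers only spontaneous births. The death of one twin in utero followed by a later delivery is not counted as a death by any of them.

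**Conclusion.** The point holds as a gap in the secondary mortality endpoint. As written, fetal loss and stillbirth are not compared between arms, and the neonatal-death comparison can attenuate a true survival benefit or, under some splits, reverse it. In the illustration, a 29-point difference in total loss (57% against 28%) becomes, at 50% expectant loss before birth, anything from a 9-point excess with cerclage to a 10-point benefit per live birth (14.3% against 23.3% to 4.2%). Per fetus it runs from a 15-point excess to a 4-point benefit (7.1% against 21.9% to 3.1%).

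These figures rest on a series of 23 women, on reading its survival percentages as counts of all fetuses, on treating every delivery before 24 weeks as a loss before live birth, and on assumed cerclage shares of 6% to 25%. They show that the direction is not determined by the endpoint as defined; they do not predict a reversal. The primary endpoint and the sample size are unaffected. The change is worth making because it is cheap, not because the trial fails without it.

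**What to change.** In 3.3 and 7.2, define the mortality endpoint as *fetal loss or stillbirth after randomisation, or neonatal death before discharge*. Score it for both fetuses of every randomised woman, with the woman as the unit of analysis (0, 1 or 2 losses). Widen the mortality wording of objective 2.2 to match. Keep neonatal death among live births as a descriptive breakdown, with its definition and denominator stated. While editing, reconcile the death component of the composite, which appears in 3.3 but not in 7.2.

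With this endpoint the illustration reads 57% against 28% wherever the losses fall, and the classing of a previable live birth no longer matters.

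The cost is a few lines of wording. Pregnancy and newborn outcomes are already to be abstracted under 4.3 (item 10) and 6.5. The reported rate will be higher than a neonatal-death rate and not directly comparable with series that report neonatal deaths only. The trial is not sized for it. For 58% against 28.2% with 26 women per arm, taking the effective number per arm as 52/(1 + ICC), power is 88%, 72%, 63% and 59% at a within-pair correlation of 0, 0.5, 0.8 and 1. The documents give no value for that correlation. The endpoint should stay secondary.

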4.1 Inclusion Criteria

1. Pregnant women more than 18 years of age
2. Diamniotic twin pregnancy (limits the participants to female gender)
3. Asymptomatic
4. Cervical dilation 1- 5 cm and/or visible membranes by pelvic exam or speculum exam on second trimester ultrasound between 16-23 6/7 weeks gestation

4.2 Exclusion Criteria

1. Singleton or higher order than twins multiple gestation
2. Cervical dilation more than 5 cm
3. Amniotic membranes prolapsed into the vagina, unable to visualize cervix
4. Fetal reduction after 14 weeks from higher order
5. Monoamniotic twins
6. Twin-twin transfusion syndrome
7. Ruptured membranes prior to randomization
8. Major fetal structural anomaly
9. Fetal chromosomal abnormality
10. Cerclage already in place for other indication
11. Active vaginal bleeding
12. Suspicion of chorioamnionitis
13. Placenta previa
14. Painful regular uterine contractions
15. Labor

[figure not shown]
4.3 Subject Recruitment and Screening

1. Potential study subjects will be identified from 2 different sources:

- 1.1. Transvaginal ultrasound cervical length will be offered at the time of a routine second trimester fetal anatomy ultrasound exam. Patients with twin gestations between 18 and 23 6/7 weeks will be asked to give consent to have their cervical length measured using transvaginal ultrasound, prior to the routine ultrasound. This ultrasound is already performed as part of the PREVENTION OF PRETERM BIRTH WITH A PESSARY IN TWIN GESTATIONS “POPPT TRIAL” (IRB Control # 14D.216) which has been approved by IRB. We will use the recommended guidelines published by the Pregnancy Foundation (www.pregnancyfoundation.org/CLEAR), called CLEAR. Sonographers who will be performing screening TV ultrasounds at all sites will be certified through CLEAR or equivalent before the start of the study. After discussing the ultrasound findings, a woman with suspected cervical dilation at time of the ultrasound evaluation will have a pelvic exam with speculum in a private room. This exam would be standard care for a woman found to have a dilated cervix, preterm.
- 1.2. Patients presenting to the Emergency Room or Labor and Delivery (TJUH 7th floor) between 16-23 6/7 weeks gestation, which may require a pelvic evaluation as part of their triage assessment.
2. If the patient meets inclusion criteria (dilated cervix 1-5 cm and/or visible membranes during the speculum exam), she will be admitted to labor and delivery for observation and counseling by an obstetrician regarding the risks of preterm birth as per standard of care. Standard of care at TJUH includes observation for 24 hours to rule out active labor and/or intrauterine infection (persistent uterine contractions with progression of cervical dilation).

3. If the patient remains asymptomatic with no signs of labor, intrauterine infection or preterm rupture of membranes, she will be approached by research personnel, in a private room, to review the research protocol, risks, benefits and alternatives and implications of randomization. The patient will be given ample time to have all questions addressed and consider participation.
4. **Randomization:** If the patient agrees to participate in the study, the informed consent form will be signed and a copy will be given to the patient. Subjects with dilated cervix 1-5 cm and visible membranes who are eligible and consent to participate in the study will be randomly assigned to one of two groups: Cervical cerclage or standard obstetric management. Subjects will be randomized using blocks of randomly varying size (e.g., 2, 4 and 6).
5. **Insurance precertification:** for those patients assigned to cerclage, an insurance precertification process will be requested. If the patient doesn't have insurance, a medical necessity letter will be provided, coverage will be requested and financial office will be consulted. The patient will be notified of the precertification outcome. At this time, insurance companies are routinely covering the procedure and the costs associated with it.
6. **Cervical cerclage:** After insurance approval, cerclage will be scheduled in the operating room under anesthesia. Amniocentesis prior to the cerclage to rule out chorioamnionitis, surgical technique, type of suture, medications and maternal physical activity after surgery will be at the discretion of the surgeon.
7. After randomization, subjects will continue with their usual clinical prenatal visits, and will participate in the study until delivery. The study investigator will communicate with the subject's primary obstetrician and cerclage placement will be done by the study investigator. The primary obstetrician will be responsible for all prenatal care. Subjects will be given a phone number to call if they have any questions or concerns about the cerclage or the study. A physician who is knowledgeable about the study will be available at all times.
8. **Interim Contacts:** Subjects in both groups will be contacted by the research assistants monthly either by phone or in person at the time of their prenatal visit. The research assistants will ask the subjects if they have had any complications with their pregnancy including any evaluations and/or admissions for preterm labor, preterm contractions, vaginal discharge, vaginal bleeding or discomfort. (see appendix #1 and #2 for questionnaire)
9. **Cervical cerclage removal:** cerclage will be removed during the 36th week of pregnancy if the subject remains asymptomatic, but it may be removed earlier if indicated. Cervical cerclage can be removed by her primary physician in the office. Some reasons for early removal include active vaginal bleeding, preterm labor with persistent contractions and advanced cervical dilatation despite tocolysis, severe subject discomfort or subject request. Cervical cerclage removal involves: 1) sterile speculum exam, 2) identification of the knot of the suture or tape at the anterior lip of the cervix, 3) gentle traction of the suture and cut with scissors one side of the tape and pulling the tape out of the cervix, 4) expected discomfort associated with the speculum exam, pressure when pulling the suture/tape and minimal bleeding (one tablespoon).
10. **Pregnancy Outcome:** After subjects have completed the study and delivered, information regarding labor and delivery, and the outcome of the pregnancy, will be abstracted from the subjects' medical records. Medical release form will be signed at time of enrollment to obtain information about pregnancy outcome from medical records including prenatal care visits, ultrasound reports, labor and delivery and outcome of the newborns. In case the woman transfers her care or delivers at a different institution, the medical form release will be used to collect data from outside institution.
11. **If patient declines participation** and she is stable, she will be discharged home and continue weekly outpatient prenatal care visits. If patient elects to have expectant management (standard obstetric

management) and declines participation in the study, she may choose to participate at a later time (up to 23 6/7 weeks), if she still meets inclusion criteria. A contact number of the research personnel will be provided.

5 Study

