5.2.1 Physical exam indicated cerclage

For those randomized to physical exam indicated cerclage placement, the surgical procedure will be scheduled in the operating room under anesthesia prior to insurance precertification.

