6.2 Randomization

Patients with dilated cervix and visible membranes who are eligible and consent to participate in the study will be randomly assigned to one of two groups: Physical exam indicated cerclage or standard expectant obstetric management. Subjects will be randomized using random block sizes of four. Patients allocated to the physical exam indicated cerclage group will have the cerclage surgically placed.

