10.2 Auditing and Inspecting

The investigator will permit study-related monitoring, audits, and inspections by the EC/IRB, government regulatory bodies, and University compliance and quality assurance groups of all study related documents (e.g. source documents, regulatory documents, data collection instruments, study data etc.). The investigator will ensure the capability for inspections of applicable study-related facilities (e.g. pharmacy, diagnostic laboratory, etc.).

Participation as an investigator in this study implies acceptance of potential inspection by government regulatory authorities and applicable University compliance and quality assurance offices.

11. Ethical Considerations

This study is to be conducted according to US and international standards of Good Clinical Practice (FDA Title 21 part 312 and International Conference on Harmonization guidelines), applicable government regulations and Institutional research policies and procedures.

This protocol and any amendments will be submitted to a properly constituted independent Ethics Committee (EC) or Institutional Review Board (IRB), in agreement with local legal prescriptions, for formal approval of the study conduct. The decision of the EC/IRB concerning the conduct of the study will be made in writing to the investigator and a copy of this decision will be provided to the sponsor before commencement of this study. The investigator should provide a list of EC/IRB members and their affiliate to the sponsor.

All subjects for this study will be provided a consent form describing this study and providing sufficient information for subjects to make an informed decision about their participation in this study. This consent form will be submitted with the protocol for review and approval by the EC/IRB for the study. The formal consent of a subject, using the EC/IRB-approved consent form, must be obtained before that subject undergoes any study procedure. The consent form must be signed by the subject or legally acceptable surrogate, and the investigator-designated research professional obtaining the consent.

12. Conflict of Interest

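### Sections 4.3 and 5.2.1 disagree on whether cerclage waits for the insurer, and under 4.3 the payer step begins only after randomisation and only in the cerclage arm

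*Combined protocol and SAP*

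**What the plan says.** Section 4.3 sets out a sequence. In item 4 a woman who agrees to take part signs consent ("the informed consent form will be signed and a copy will be given to the patient") and is randomised. In item 5, "for those patients assigned to cerclage, an insurance precertification process will be requested". In item 6, "After insurance approval, cerclage will be scheduled in the operating room under anesthesia".

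Item 5 also provides for a woman without insurance: "a medical necessity letter will be provided, coverage will be requested and financial office will be consulted". The patient is told the result. On the likelihood of cover, the same item says "At this time, insurance companies are routinely covering the procedure and the costs associated with it".

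Section 5.2.1, describing the same arm, says that "the surgical procedure will be scheduled in the operating room under anesthesia prior to insurance precertification".

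Sections 4.3, 5.2.1, 5.4 and 6.2 do not say what happens if cover is refused, and they set no longest acceptable time from randomisation to placement. Section 7.2 specifies intention-to-treat analysis and a Kaplan-Meier analysis that runs from randomisation.

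**The concern.** Two operative sections give opposite orders for the same step. In most trials this would be a clerical matter. Here the operation is urgent. Section 1.1 calls second-trimester dilation the worst prognostic factor for preterm birth, and Section 1.3 lists advanced dilation as a reason why cerclage may fail to be placed. Section 4.3 observes women for 24 hours, to exclude labour and infection, before they are approached. A wait of unspecified length after assignment lets those conditions develop again, and only in the arm that needs an operation.

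Two things are at stake. The first is safety and clarity: site staff need to know whether to hold a patient for an insurer. The second is the treatment contrast: a woman who progresses or is refused while approval is pending is analysed as cerclage although she may have received only expectant care.

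**Working it through.** **1. The two instructions side by side.**

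| Place | Order stated | Does placement wait for the payer? |
|---|---|---|
| 4.3 items 4–6 | randomise, request, approval, schedule surgery | Yes: surgery cannot precede its own scheduling |
| 5.2.1 | schedule surgery, then precertification | Not stated: scheduling does not wait |

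Both sentences concern scheduling. They cannot both be followed.

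**2. Possible readings.**
- *5.2.1 is a slip for the 4.3 order.* Then 4.3 governs and surgery waits for approval, with no limit on the wait and no refusal rule.
- *5.2.1 is intended.* Then 4.3 item 6 is wrong and needs correcting.
- *5.2.1 means that a slot is booked early but used only once approved.* Then placement still waits, with the same gaps.

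Under every reading at least one sentence has to change. Under two of the three, the unbounded wait remains.

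**3. Effect on the comparison.** Section 7.1 assumes event rates of 80% and 40%. Suppose a fraction *f* of the cerclage arm never receives a cerclage and has the control risk (an assumption). Then:

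- cerclage-arm rate = 0.40 + 0.40 *f*
- expected difference = 0.80 − (0.40 + 0.40 *f*) = 0.40 (1 − *f*)

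The direction is towards no difference. The documents give no value for *f* and no delay distribution, so the size cannot be derived from them. A short delay without progression need not change the effect at all.

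**4. Effect on validity.** Women stay in their assigned arm, and follow-up in the time-to-event analysis starts at randomisation. Neither refusal nor delay removes anyone from the comparison or creates a period in which events cannot be counted.

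**5. The plan's sample size and the cost of the remedy.** With pooled variance, two-sided 5% and 80% power:

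n per arm = [1.96 √(2 × 0.6 × 0.4) + 0.842 √(0.8 × 0.2 + 0.4 × 0.6)]² / 0.4² = (1.358 + 0.532)² / 0.16 ≈ 22.3, rounded up to 23.

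That gives 46 in total, and 46 / 0.90 = 51.1, rounded up to 52. The plan's figures reproduce and are not in dispute here. Requests under 4.3 number about 52 / 2 = 26. Requests for all randomised women would be 52, which is 52 − 26 = 26 more, plus any for women who consent but are not randomised.

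**The case against.** **Coverage is routine and uninsured women have a route.** This stands as to frequency: refusals are probably few. It does not limit the length of the wait, and the route for uninsured women stops at a consultation with no stated outcome.

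**5.2.1 may be a drafting slip.** Quite possibly. Correcting that phrase alone would leave the operation waiting on the payer.

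**A refusal rule may sit in the consent form.** It may. That form is not part of the text reviewed, so the absence noted here is limited to the protocol sections named.

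A reader might also infer three stronger points that the documents do not support.

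- *That Section 6.2 is a third conflicting instruction.* It says "Patients allocated to the physical exam indicated cerclage group will have the cerclage surgically placed". This is a summary of allocation. Not mentioning insurance does not contradict 4.3.
- *That the trial loses a definite amount of power.* With 26 per arm, and 0, 1 or 2 cerclage-arm women untreated at 80% risk, the expected difference is 40.0, 38.5 or 36.9 points and exact Fisher power is 79.9%, 76.8% or 73.3%. The arithmetic is sound, but the counts are invented and the loss would be the same for non-receipt from any cause. The 40% in Section 7.1 is not said to assume complete receipt, so it may already allow for failed placements. These figures are not evidence about insurance.
- *That the analysis is biased because only one arm has the step.* Expectant care has no operation to precertify, and intention-to-treat from randomisation remains valid.

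**Conclusion.** The conflict between 4.3 item 6 and 5.2.1 is plain on the text. Following 4.3 as written builds an avoidable chance of delay or non-receipt into the cerclage arm. The consequence is dilution of the contrast, plus a safety question for the individual woman. Its size is unknown and probably small, a judgement that rests on the protocol's own statement about routine coverage and not on any rate. It is worth correcting because the correction is inexpensive, not because the trial's validity depends on it.

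**What to change.** 1. In 4.3, divide item 4. After consent is signed and before assignment, file the precertification or financial-office request for every consenting woman, then randomise without waiting for the answer. Confirmed funding should **not** become an enrolment condition: in a rare and urgent condition that would lose women who progress while waiting, and would select on coverage. The request should follow consent, in keeping with Section 11, which says that consent "must be obtained before that subject undergoes any study procedure". The consent form should mention the request.
2. Remove the opening clause of 4.3 item 6 and the closing phrase of 5.2.1. Put the same sentence in both places: after assignment, cerclage is placed within a maximum interval of [the investigators' figure] and does not wait for the payer decision.
3. State who bears the cost if cover is refused.

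The documents offer no basis for a particular interval, so the investigators must choose it on clinical grounds.

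Cost: edits to two sections and a line in the consent form, about 26 more coverage requests, and payment for the occasional refused case.
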